7.4.2 Collection of Samples for B and T Lymphocyte Analysis

Blood samples will be collected for quantification of B and T lymphocyte subsets on Day 1 (prior to dosing) and Day 15 of Cycles 1 and 2 as outlined in [Table 6-1](#).

8 Adverse Event Reporting

8.1 Definitions

ADVERSE EVENT (EXPERIENCE) - any unfavorable or unintended sign, symptom, or disease that is temporally associated with the use of a study agent but is not necessarily caused by the study agent. This includes worsening (eg, increase in frequency or severity) of pre-existing conditions.

SERIOUS ADVERSE EVENT – an adverse event resulting in any of the following outcomes:

- death
- is life threatening (ie, an immediate threat to life)
- inpatient hospitalization
- prolongation of an existing hospitalization
- persistent or significant disability / incapacity
- congenital anomaly / birth defect
- is Medically Important*

*Medical and scientific judgment will be exercised in deciding whether expedited reporting is appropriate in other situations, such as important medical events that may not be immediately life threatening or result in death or result in hospitalization but may jeopardize the patient or may require intervention to prevent one of the other outcomes listed above. These should also usually be considered serious. (ICH guidelines, March 1995)

Note: Hospitalizations not associated with an adverse event, for example, for administration of chemotherapy or hydration for chemotherapy administration, are not considered serious adverse events.

UNEXPECTED ADVERSE EVENT - An adverse event, the nature or severity of which is not consistent with the applicable product information (eg, Investigator's Brochure for an unapproved investigational product or package insert/summary of product characteristics for an approved product). Expected means that the event has previously been observed with the study agent and is identified and/or described in the applicable product information. It does not mean that the event is expected with the underlying disease(s) or concomitant medications.

8.2 Reporting Adverse Events to the Sponsor or Designee

The investigator and their designees are responsible for detecting, documenting and reporting events that meet the definition of an AE or SAE.

AM03
15Jul15

Any SAEs assessed as related to study participation (e.g., protocol-mandated procedures, invasive tests, or change in existing therapy) or related to a Human Genome Science product will be recorded from the time a subject consents to participate in the study up to and including any follow-up contact.

Investigators are not obligated to actively seek AEs or SAEs in former study subjects. However, if the investigator learns of any SAE, including a death, at any time after a subject has been discharged from the study, and he/she considers the event reasonably related to the study treatment or study participation, the investigator must promptly notify GSK CMG.

All adverse events (AEs) that are identified from the start of any study agent administration through the specified study follow-up period (through 30 days following administration of the final study agent dose) will be recorded on the paper/electronic Adverse Event Case Report Form (AE case report form). All data fields on the AE case report form will be completed.

Serious Adverse Events (SAEs) must ALSO be recorded on the SAE Worksheet and emailed to GSK CMG at **PPD** (fax backup: **PPD**) within 24 hours of site personnel becoming aware of a SAE, regardless of expectedness. All pages of the SAE Worksheet will be completed, but the SAE worksheet will not be held until all information is available. Additional information and corrections will be provided on subsequent SAE Worksheets as described in the Study Procedure Manual.

8.3 Laboratory Abnormalities as Adverse Events

A laboratory abnormality will be reported as an adverse event if it is associated with an intervention. Intervention includes, but is not limited to, discontinuation of treatment, dose reduction/delay, additional assessments (excluding follow-up labs), or concomitant therapy. In addition, any medically important laboratory abnormality may be reported as an adverse event at the discretion of the investigator. This includes laboratory abnormalities for which there is no intervention but the abnormal value(s) suggests a disease or organ toxicity. If clinical

sequelae are associated with a laboratory abnormality, the diagnosis or medical condition will be reported (eg, renal failure, hematuria) not the laboratory abnormality (eg, elevated creatinine, urine red blood cells increased).

8.4 Other Events Requiring Rapid Reporting

Protocol Specified Events are additional events [toxicities] specifically identified in this protocol that must be reported to GSK CMG or designee in an expedited manner. Protocol Specified Events may or may not be SAEs as defined in this protocol. They are SAEs if they meet one or more of the criteria for an SAE (see Section 8.1). Protocol Specified Events are recorded on SAE Worksheets and sent to GSK CMG within 24 hours of site personnel becoming aware of the event.

The Protocol Specified Events for the study:

- Grade 4 neutropenia for > 7 consecutive days or febrile neutropenia.
- Grade 4 thrombocytopenia.
- Grade 3 or greater non-hematologic AEs except transaminase, amylase and lipase abnormalities for which the following criteria apply:
 - Grade 4 elevations in transaminases.
 - Grade 4 elevations in lipase or amylase.
 - Grade 3 elevations in lipase or amylase associated with clinical/imaging findings of pancreatitis, resulting in chronic damage to the pancreas.
- Any adverse event that results in discontinuation of treatment if that event is assessed as possibly, probably, or definitely related to mapatumumab or sorafenib.

AM01
21Dec10

8.5 Reporting a Pregnancy

Any pregnancy in a female participant or a female partner of a male participant must be reported to GSK CMG as soon as the site becomes aware of the pregnancy. All pregnancies are reported up to 30 days following the last study agent treatment. GSK CMG sends an acknowledgement memorandum to the principal investigator along with a Pregnancy Assessment Form. Additional Pregnancy Assessment Forms will be sent to the site every 3 months for reporting of follow-up information. Pregnancy assessment forms must be completed by the investigator until live birth, elective termination of the pregnancy, or miscarriage. The site is responsible for following the subject's pregnancy to final outcome.

Pregnancies are not considered adverse events. Complications or medical problems associated with a pregnancy are considered AEs and may be SAEs. Complications or medical problems are reported as AEs/SAEs according to the procedure described in Section 8.2.

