19. Pregnant female or nursing mother. All females with an intact uterus (unless amenorrheic for the 24 months before enrollment) must have a negative serum pregnancy test at screening. All non-sterile or non-postmenopausal females must practice a medically accepted method of contraception over the course of the study and for 60 days after the last dose of study agent.
20. Males who do not agree to use effective contraception during the study and for a period of 60 days following the final dose of study agent.
21. Subject is currently enrolled in or has not yet completed at least 30 days since ending other investigational device or drug study(s) or subject is receiving other investigational agents.
22. Acute or chronic severe renal insufficiency (glomerular filtration rate < 30 mL/min/1.73 m²) or acute renal insufficiency of any severity due to the hepato-renal syndrome.
23. Hepatitis B virus DNA levels $> 2,000$ IU/mL.

Study Design and Schedule:

This is a Phase 2, multi-center, randomized, double-blind, placebo-controlled study to evaluate the efficacy and safety of mapatumumab in combination with sorafenib in subjects with advanced hepatocellular carcinoma. In addition to receiving sorafenib, subjects will be randomly assigned to 1 of 2 treatment groups in a 1:1 ratio to receive 30 mg/kg mapatumumab or placebo.

Randomization will be stratified according to BCLC advanced stage C vs BCLC intermediate stage B and ECOG performance status (0 vs 1, 2).

Approximately 100 advanced HCC subjects will be randomized/enrolled.

Study Treatment:

Mapatumumab will be supplied in open label vials and third party unblinding will be employed. The study agent will be reconstituted by the unblinded site pharmacist or unblinded designee. The unblinded site pharmacist or unblinded designee will also be the person responsible for receiving and dispensing study agent but independent of all other study activities. All other study personnel, the subject, the Sponsor will remain blinded to the study agent received. Separate monitors will be responsible for the clinical (blinded monitor) and study agent (unblinded monitor) aspects of the study.

Subjects will receive treatment every 21 days (ie, a cycle) as outlined below:

Arm A: Sorafenib 400 mg orally twice daily continuously in each cycle + placebo intravenously on Day 1 of each cycle.

Arm B: Sorafenib 400 mg orally twice daily continuously + mapatumumab (30 mg/kg) intravenously on Day 1 of each cycle.

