15. Unstable angina, myocardial infarction, cerebrovascular accident, \geq Class II congestive heart failure according to the New York Heart Association Classification for Congestive Heart Failure (see [Appendix 4](#)) within 6 months before enrollment.
16. Cardiac arrhythmias requiring anti-arrhythmic therapy other than beta blockers or digoxin.
17. Uncontrolled hypertension (systolic blood pressure > 150 mmHg or diastolic pressure > 90 mmHg despite optimal medical management).

AM02
23Feb11

18. Using and unable to discontinue use of concomitant strong CYP3A4 inducers (eg, including but not limited to St. John's Wort, dexamethasone, phenytoin, carbamazepine, rifampin, rifabutin, phenobarbital).
19. Pregnant female or nursing mother. All females with an intact uterus (unless amenorrheic for the 24 months before enrollment) must have a negative serum pregnancy test at screening. All non-sterile or non-postmenopausal females must practice a medically accepted method of contraception over the course of the study and for 60 days after the last dose of study agent.
20. Males who do not agree to use effective contraception during the study and for a period of 60 days following the final dose of study agent.
21. Subject is currently enrolled in or has not yet completed at least 30 days since ending other investigational device or drug study(s) or subject is receiving other investigational agents.
22. Acute or chronic severe renal insufficiency (glomerular filtration rate $< 30 \text{ mL/min/1.73 m}^2$) or acute renal insufficiency of any severity due to the hepato-renal syndrome.
23. Hepatitis B virus DNA levels $> 2,000 \text{ IU/mL}$.

5 Study Treatment Regimen

Sorafenib will be administered at a dose of 400 mg twice daily without food (at least 1 hour before or 2 hours after a meal). On days when both sorafenib and mapatumumab/placebo are administered together, the sorafenib should be taken at the same time as any other calendar day.

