6.3 On-treatment Study Procedures

Table 6-1 Study calendar

Procedure	Footnotes	Screen Phase	Cycle 1					Cycle 2					Additional Cycles ¹³			Extended Access Phase	Safety Follow-up Phase
			Day 1	Day 2	Day 3	Day 8	Day 15	Day 1	Day 3	Day 8	Day 15	Day 1	Day 8	Day 15			
Informed consent		X														X	
Laboratory																	
CBC with differential; Coagulation parameters	1	X	X	X	X	X	X	X	X	X	X	X	X	X	X		
Chemistry	1	X	X	X	X	X	X	X	X	X	X	X	X	X	X		
Pregnancy	2	X	X														
Hepatitis	1	X															
B and T lymphocyte subsets	3		X					X	X			X					
Immunogenicity	4		X					X				X					
Pharmacokinetics	5		X			X		X				X					
Biomarkers	6		X	X	X	X	X	X	X	X	X						
Study Agent Admin																	
Sorafenib	7							Twice daily					X				
Mapatumumab/Placebo	7		X					X				X			X		
Physical/Clinical																	
Med Hx / Phys.Exam	-	X															
Vital signs	8	X	X			X	X	X		X	X	X			X		
Body weight	9	X	X					X				X					
Performance Status	10	X	X					X				X					
Record AEs/	11	X											<-----Throughout the study----->				

Table 6-1 Study calendar

Procedure	Footnotes	Screen Phase	Cycle 1				Cycle 2				Additional Cycles ¹³			Extended Access Phase	Safety Follow-up Phase
			Day 1	Day 2	Day 3	Day 8	Day 15	Day 1	Day 3	Day 8	Day 15	Day 1	Day 8	Day 15	
Conmeds															
Disease Assessments	12	X	Performed at the end of every 2 cycles (ie, Cycles 2, 4, 6) and every 2 cycles thereafter until radiologic PD is documented.										X		
α – Fetoprotein (AFP)	12	X	Performed at the end of every 2 cycles (ie Cycles 2, 4, 6) and every 2 cycles thereafter until radiographic PD is documented.												
ECG	-	X	Repeat as clinically indicated												

AE = adverse event; CBC = complete blood count; CT = computerized tomography; ECG = electrocardiogram; PD = progressive disease.

- ¹ Safety Labs: Day 1 (complete blood count with differential, coagulation parameters [INR, PT, PTT] and chemistry) must be performed within 3 days prior to dosing on Day 1 of each cycle. See [Appendix 7](#) for a detailed list of required laboratory assessments.
- ² Pregnancy: Serum test at screening, urine test pre-dose Cycle 1 Day 1; must be negative to receive treatment.
- ³ B and T lymphocyte subsets: Blood samples for quantification of B and T lymphocytes will be obtained in Cycles 1 and 2 only. Samples will be obtained on Day 1 (prior to dosing) and Day 15 of Cycles 1 and 2.

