6.5 Safety Follow-up

After discontinuation of study treatment, all subjects will return at least 30 days after the last dose of sorafenib and/or mapatumumab/placebo, for scheduled safety follow-up assessments as outlined in [Table 6-1](#).

AM03
15Jul15

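### Pregnancy reporting carries an unclear 30-day limit while contraception is required for 60 days, so reporting in days 31 to 60 is not clearly required

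*Protocol*

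**What the plan says.** Two consecutive sentences in Protocol Section 8.5 set the reporting duty. One says that any pregnancy in a woman in the trial, or in the partner of a man in the trial, "must be reported to GSK CMG as soon as the site becomes aware of the pregnancy". The other says: "All pregnancies are reported up to 30 days following the last study agent treatment". A report sets off the Pregnancy Assessment Form, further forms every three months, and follow-up by the site to the outcome. The same section says that a pregnancy is not an adverse event (AE), although its complications are AEs and may be serious.

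The contraception period is in Section 4.2. Criterion 19 requires of women an accepted "method of contraception over the course of the study and for 60 days after the last dose of study agent". Criterion 20 requires of men "effective contraception during the study and for a period of 60 days following the final dose of study agent". The synopsis repeats both.

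Three other provisions bear on what a site would learn after treatment stops:

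- Safety visit (Section 6.5): "all subjects will return at least 30 days after the last dose of sorafenib and/or mapatumumab/placebo".
- Pregnancy testing (Table 6-1, footnote 2): "Serum test at screening, urine test pre-dose Cycle 1 Day 1; must be negative to receive treatment".
- Events learned of after discharge (Section 8.2): the investigator must notify a serious adverse event (SAE) if it is considered reasonably related to study treatment or participation.

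Neither the protocol nor the SAP explains why one period is 30 days and the other 60.

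**The concern.** The protocol asks participants to avoid conception for twice as long as it clearly asks sites to report one. If a precaution is worth imposing for 60 days, a pregnancy in that period is one the sponsor would want to know about. What is at stake is safety information: whether a pregnancy in the second month after treatment is reported and followed to outcome.

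The point is not confined to women of child-bearing age in the trial. Section 8.5 covers partners of male participants, criterion 20 places the same 60 days on men, adults are eligible from age 18, and Section 1.1 describes the disease as more common in men.

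Section 8.5 is also unclear in itself. An open-ended duty is followed at once by a limit, and the limit does not name the event it applies to.

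**Working it through.** The plan states no figure to reproduce. The check compares two stated periods and then asks whether any other provision covers the difference.

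**Inputs**
- Contraception after the last dose: 60 days, women and men (Protocol Section 4.2, criteria 19 and 20; synopsis).
- Pregnancy reporting limit: 30 days (Protocol Section 8.5, second sentence).

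**Difference**
- 60 − 30 = 30 days, namely days 31 to 60.
- As a share of the contraception period: (60 − 30) / 60 = 50%. This is a ratio of two administrative periods, not a share of risk.

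**What falls outside, by reading of Section 8.5**
1. The awareness sentence governs and the limit does not restrict it: nothing falls outside.
2. The limit applies to conception: conceptions in days 31 to 60 fall outside. Conceptions up to day 30 are covered even if recognised later.
3. The limit applies to detection or site awareness: anything recognised after day 30 falls outside, including a conception during treatment or in the first 30 days after it. The gap can then exceed 30 days' worth of conceptions.

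The text does not decide between these readings.

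**Whether another provision covers days 31 to 60**
- Scheduled pregnancy tests end at Cycle 1 Day 1, so none falls after treatment.
- The safety visit has a minimum of 30 days and no requirement to reach day 60. AE recording (Section 8.2), AE follow-up (Section 8.7) and safety collection after withdrawal (Section 6.6) also run to 30 days.
- Table 6-1, footnote 12, keeps six-weekly imaging for subjects who stop treatment before radiologic progression. Those visits are a chance to hear of a pregnancy, but they include no pregnancy question or test and do not apply to subjects who stop because of progression. Amendment 3 removed the long-term follow-up phase (Appendix 9).
- The after-discharge rule in Section 8.2 covers SAEs judged related. A related serious complication would qualify, as would a related congenital anomaly, which Section 8.1 lists as an SAE outcome. An uncomplicated pregnancy would not qualify, nor would a complication judged unrelated.

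On readings 2 and 3, nothing else requires a pregnancy arising in days 31 to 60 to be reported.

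**The case against.** The strongest reply is that the sentence before the limit is unconditional: a site that learns of a pregnancy must report it, whenever that is. This stands to the extent that a reader who infers that pregnancies in days 31 to 60 go unreported is going too far. A site could report them and be following Section 8.5. It does not remove the point, because the next sentence sets a limit and sites are left to choose between the two.

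A second reply is that the 60 days is a contraception precaution written as an eligibility criterion, while the 30 days matches the rest of the safety collection. One period prevents conception and the other collects data, and a site can comply with both. This also stands. A reader might infer that 60 days is the protocol's declared exposure-risk period and that half of the risk is left uncovered. The protocol declares no such period and does not say how the 60 days was chosen. What remains is that the two periods concern the same event, pregnancy after exposure, and no reason is given for collecting over the shorter one.

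A third reply is that the after-discharge rule already catches the serious outcomes. It catches the related ones, provided that the investigator hears of them. It does not start the pregnancy forms or the follow-up to outcome.

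A fourth is that the number of events will be close to nil. That is probably right, and it sets the priority of the point; it does not make the text clear.

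**Conclusion.** The point holds as a minor one. As written, the protocol does not clearly require a pregnancy in days 31 to 60 after the last dose to be reported or followed to outcome, whether in a participant or in a male participant's partner. If the 30-day limit refers to detection or awareness, some earlier conceptions are in the same position.

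The conclusion rests on one assumption: that the second sentence of Section 8.5 is meant to limit the one before it. If the sponsor intended reporting to be open-ended, the defect is only one of wording.

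The documents give no pregnancy rate, so no event count is estimated. With about 100 subjects planned it should be very small. Appendix 9 says that at least 90% of subjects had met the survival endpoint by Amendment 3, so few remain to whom a change would apply. The earlier protocol versions contain the same two periods, so the mismatch did not arise with Amendment 3. The TTP analysis, the secondary efficacy analyses and the sample size are unaffected.

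**What to change.** Reconcile Sections 4.2 and 8.5. Which contraception period is appropriate is a clinical matter for the sponsor and is not judged here. Whatever period Section 4.2 states, Section 8.5 should:

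- make the passive reporting window at least as long, preferably by cross-reference to Section 4.2 so that the two cannot drift apart;
- say whether the window refers to conception, detection or site awareness. Conception makes it directly comparable with the contraception period; detection or awareness would need a longer window to cover the same conceptions;
- merge the two reporting sentences, so that a site knows what to do with a pregnancy it learns of late.

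The cost is a short text change and perhaps a few extra passive reports, each with its forms and follow-up. No visits or tests are added. The change would capture only what sites come to hear of. Systematic ascertainment to day 60 would need an added contact or test, which is not proposed here.

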8.6 Investigator Evaluation of Adverse Events

The Investigator will evaluate all adverse events with respect to seriousness (criteria listed in Section 8.1 above), severity (intensity or grade) and causality (relationship to study agent) according to the following guidelines listed below.

SEVERITY

Severity will be graded using the NCI-CTCAE, Version 4.0. The NCI-CTCAE may be downloaded from the Cancer Treatment Evaluation Program website (<http://ctep.info.nih.gov/reporting/ctc.html>). In the event that an AE does not have an NCI-CTCAE code, the following severity classifications will be used:

Mild	causing no limitation of usual activities
Moderate	causing some limitation of usual activities
Severe	causing inability to carry out usual activities
Life Threatening*	potentially life threatening or disabling

***Note** – a severity assessment of life threatening is not necessarily the same as life threatening as a “Serious” criterion. The latter means that the event is an immediate threat to life as opposed to a potential threat to life.

CAUSALITY

Definitely Related	reasonable temporal relationship to study agent administration follows a known response pattern (eg, drug is known to cause this AE) there is no alternative etiology
Probably Related	reasonable temporal relationship follows a suspected response pattern (eg, based on similar drugs) no evidence for a more likely alternative etiology
Possibly Related	reasonable temporal relationship little evidence for a more likely alternative etiology
Probably Not Related	does not have a reasonable temporal relationship, OR good evidence for a more likely alternative etiology
Not Related	does not have a temporal relationship, OR definitely due to alternative etiology

ICH guidelines (March, 1995) clarify “reasonable causal relationship” to mean “that there are facts [evidence] or arguments to suggest a causal relationship”.

The causality assessment must be made by the investigator based on information available at the time that the SAE worksheet is completed. The initial causality assessment may be revised as new information becomes available.

***Note** - If there is evidence that mapatumumab/placebo contributed to or exacerbated an event related to sorafenib; the event will be recorded as possibly, probably or definitely related to both sorafenib and mapatumumab.

